7.6 Regulatory Reporting Requirements for Serious Adverse Events

The Sponsor/designee will send appropriate safety notifications to Health Authorities in accordance with applicable laws and regulations.

The Investigator must comply with any applicable site-specific requirements related to the reporting of SAEs (particularly deaths) involving study subjects to the IEC/IRB that approved the study.

In accordance with International Council for Harmonisation (ICH) Good Clinical Practice (GCP), the Sponsor/designee will inform the Investigator of findings that could adversely affect the safety of subjects, impact the conduct of the study, or alter the IEC's/IRB's approval/favorable opinion to continue the study. In line with respective regulations, the Sponsor/designee will inform the Investigator of AEs (and ADE's) that are both serious and unexpected/unanticipated and considered to be related to the administered product (SUSARs/USADEs). The Investigator should place copies of Safety Reports in the Investigator Site File. National regulations regarding Safety Report notifications to Investigators will be considered.

When specifically required by regulations and guidelines, the Sponsor/designee will provide appropriate Safety Reports directly to the concerned lead IEC/IRB and will maintain records of these notifications. When direct reporting is not clearly defined by national or site-specific regulations, the Investigator will be responsible for promptly notifying the concerned IEC/IRB of any Safety Reports provided by the Sponsor/designee and of filing copies of all related correspondence in the Investigator Site File.

For studies covered by the European Directive 2001/20/EC, the Sponsor's responsibilities regarding the reporting of SAEs/SUSARs/Safety Issues will be carried out in accordance with that Directive and with the related Detailed Guidance documents.

Unanticipated Serious Adverse Device Effect

An unanticipated serious adverse device effect (USADE) is any serious adverse effect on health or safety or any life-threatening problem or death caused by, or associated with, a device, if that effect, problem, or death was not previously identified in nature, severity, or degree of incidence in the investigational plan or application (including a supplementary plan or application), or any other unanticipated serious problem associated with a device that relates to the rights, safety, or welfare of subjects. A USADE is a serious adverse device effect, which by its nature, incidence,

severity, or outcome has not been identified in the current version of the Investigators' Brochure. All USADE's follow the same reporting requirements as for SUSARs.

Device Deficiency

Investigator should assess all device deficiencies for SADE (serious adverse device effect) potential. For investigational devices, reportable events include any device deficiency that might have led to an SAE if appropriate action had not been taken, intervention had not occurred, or circumstances had been less fortunate.

Procedures for Breaking the Treatment Codes

If the Investigator decides that unblinding is warranted in cases of a medical emergency where knowledge of randomization group is required, the Sponsor/CRO must be notified within 24 hours after unblinding. The Investigator must provide the CRO the reason for unblinding without revealing the study drug, except to the CRO's designated drug safety representative, as appropriate. The date of and reason for unblinding must be recorded in the source documents. Contact information for unblinding in an emergency is given on the subject emergency card provided to each subject, as noted in [Section 9.2.1](#) (Emergency Medical Support).

Treatment code unblinding is performed in the IWRS. After logging into the IWRS, the Investigator must indicate the action for "unblinding by the site". The investigator must enter the site number, subject number, and subject's year of birth. The instructions are also found in the "Blinded Site User, Blinded Investigator, Blinded Coordinator, Blinded Monitor User Guide" for the Cenduit IWRS.

In the event that the IWRS is inaccessible, the Investigator should call the Cenduit Global Helpdesk which is available 24 hours, 365 days a year. Live translation is available. The Global Helpdesk numbers are:

Toll-Free United States and Canada: [name]

Universal Free EU: [name]

Direct-Dial United States and Canada: [name]

Direct-Dial United Kingdom: [contact]

The Cenduit IWRS User Guide additionally provides an international telephone list for specific countries. The Sponsor (or delegate) will submit any Suspected Unexpected Serious Adverse Reactions (SUSAR) reports to regulatory authorities and ethics committees with unblinded information, per applicable regulations. Only blinded information will be provided to the study team.

If emergency unblinding is required for an AE/SAE/SADE, causality assessments should be documented for the AE/SAE/SADE prior to unblinding.

7.7 Management of Adverse Events Associated with Abnormal Laboratory Findings

All clinical and clinically significant laboratory toxicities will be managed according to uniform guidelines detailed in [Appendix 5](#) and as outlined below.

Grades 1 (Mild) and 2 (Moderate) Laboratory Abnormality or Clinical Event

Continue study drug at the discretion of the Investigator.

Grades 3 (Severe) Laboratory Abnormality or Clinical Event

Study drug may be continued if the event is considered to be not related to study drug.

For clinical event or clinically significant laboratory abnormality confirmed by repeat testing, that is considered to be related to study drug, study drug should be withheld until the toxicity returns to \leq Grade 2.

If a laboratory abnormality recurs to \geq Grade 3 following re-starting of study drug and is considered related to study drug and medically important by Investigator and/or Sponsor/designee, then the study drug should be permanently discontinued, and the subject managed according to local clinical practice. Recurrence of laboratory abnormalities considered not related to study drug may not require permanent discontinuation.

Grades 4 (Severe) Laboratory Abnormality or Clinical Event

For clinical event or Grade 4 laboratory abnormality confirmed by repeat testing that is considered related to study drug and medically important by the Investigator and/or Sponsor/designee, study drug should be permanently discontinued, and the subject managed according to local clinical practice. The subject should be followed as clinically indicated until the laboratory abnormality returns to baseline or is otherwise explained, whichever occurs first. A clinically significant Grade 4 laboratory abnormality that is not confirmed by repeat testing should be managed according to the algorithm for the new toxicity grade.

Study drug may be continued without dose interruption for a clinically non-significant Grade 4 laboratory abnormality (e.g., triglyceride elevation that is non-fasting or that can be medically managed) or a clinical event considered not related to the study drug.

All subjects experiencing AEs must be monitored until symptoms subside and any abnormal laboratory values have resolved, returned to baseline levels, is considered irreversible, or have a reasonable explanation for the changes observed.

7.8 Pregnancy and Contraception

It is not known whether treatment with AV-101 may cause injury or harm to an unborn child if taken during pregnancy, or if it may cause harm to a breastfeeding infant. For this reason, pregnant or breastfeeding women are not allowed to take part in the study. It is important that women avoid

getting pregnant during the study. Therefore, all women of childbearing potential taking part in the study must use a highly effective form of contraception for at least 28 days prior to when they will receive the first dose of study drug, and for at least 30 days after completing or discontinuing study treatment. All hormonal contraceptive methods used must be associated with inhibition of ovulation. Abstinence is acceptable only as true abstinence: when this is in line with the preferred and usual lifestyle of the patient. Periodic abstinence (e.g., calendar, ovulation, symptothermal, post-ovulation methods) and withdrawal are not acceptable methods of contraception.*

At the Baseline Visit, all women capable of having children will have a pregnancy test (Urine test). Women capable of having children include all women except those whose menstrual periods have not occurred for more than 1 year after menopause (change of life or postmenopausal), or those who have had sterilization surgery (tubal ligation or a complete hysterectomy and/or removal of both ovaries). Postmenopausal is defined as no menses for 12 months without an alternative medical cause. A high follicle stimulating hormone (FSH) level in the postmenopausal range at the Screening Visit may be used to confirm a postmenopausal state in women not using hormonal contraception or hormonal replacement therapy. However, in the absence of 12 months of amenorrhea, a single FSH measurement is insufficient.

In addition to pregnancy testing performed at study visits, all women of childbearing potential are provided home urine pregnancy tests to be performed every 4 weeks from the date of randomization. The tests are performed at home during the months for which a study visit does not occur. If the 4-week interval falls on a visit date, then testing is to be performed during the study visit. Women must be instructed to immediately report a positive test result to the Study Investigator.

The subject must be contacted when the test is due, and the following recorded:

In source documentation:

- Test date
- Test result
- Lot number of the test
- Expiration date of the test

In the eCRF:

- Test date
- Test result

The results are to be documented in the eCRF and in the patient file in a timely manner. It is not acceptable to obtain the result only at the next scheduled visit. In the event of pregnancy, a referral to a gynecologist for confirmation of pregnancy must be organized as soon as possible. In addition, the pregnancy must be reported to the sponsor as described in [Section 7.8.1](#), and further consequences in regard to ongoing participation in the study must be discussed with the patient. In the event there are uncertainties about a pregnancy test outcome, the patient should similarly contact the site immediately to discuss further steps e.g. exclusion of pregnancy by serum pregnancy test.

Table 4 contains a list of highly effective forms of contraception. Women who are not capable of bearing children are exempt from contraception requirements.

Table 4 Protocol Defined Highly Effective Forms of Contraception

Single Methods	Combination Methods

Intrauterine Devices (IUDs) Intrauterine hormone-releasing system (IUS)
 
Progesterone
 
 • Implant • Injection 
Tubal Sterilization
 
Bilateral oophorectomy
 
Bilateral Salpingectomy
 
Total hysterectomy
 
Vasectomy with Documented Azoospermia 3 months After the Procedure
 
*Abstinence from heterosexual intercourse (lifelong decision or at least 1 year)
	
Estrogen and Progesterone
 
 • Combined oral contraceptives • Transdermal patch • Intravaginal ring

7.8.1 Pregnancy Reporting

The Investigator must notify the CRO/designee in an expedited manner of any pregnancy using the Pregnancy Report Form, which must be transmitted by the same process specified for SAE reporting in Section 7.5.

Investigators must actively follow-up, document and report on the outcome of all pregnancies, even if the subjects are withdrawn from the study.

The Investigator must notify the Sponsor/designee of these outcomes using the Pregnancy Report Form. If an abnormal outcome occurs, the SAE Report Form will be used if the subject sustains an event and the Pregnancy Report Form if the child/fetus sustains an event. Any abnormal outcome (e.g., spontaneous abortion, fetal death, stillbirth, congenital anomalies, ectopic pregnancy) must be reported in an expedited manner, as specified in Section 7.5, while normal outcomes must be reported within 45 days after delivery.

In the event of a pregnancy in a subject occurring during the study, the subject must be discontinued from study drug. The Sponsor/designee must be notified without delay and the subject must be followed as indicated above.

7.9 Treatment of Overdose

For this study, any dose of study drug greater than 4 capsules per day will be considered an overdose, provided it can be confirmed that the subject actually dosed with extra capsules. If a subject is down titrated to one capsule, accidental dosing with two capsules will not be considered an overdose.

Even if it is not associated with an AE or an SAE, any overdose must be recorded in source documents and the appropriate CRF and reported to the Sponsor/CRO in an expedited manner according to the SAE reporting procedure in [Section 7.5](#).

The Sponsor does not recommend specific treatment for an overdose. The effects of an overdose of AV-101 are unknown and there is no known specific treatment in case of overdose. In the event of overdose, subjects should be considered for hospitalization for observation if clinically indicated, and appropriate supportive treatment should be given as needed per the Investigator's clinical judgment.

8 Statistical Considerations

This section presents an overview of the statistical analyses that will be used to meet the study objectives. Details of the statistical analyses will be provided in a statistical analysis plan (SAP).

8.1 Introduction: Study Design and Analysis Overview

The LTE is a longitudinal study of the long-term safety and effectiveness of PAH patients treated with AV-101 at different dose levels until being transitioned to the optimal dose of AV-101 which is selected after the completion of the Phase 2b Part of Study AV-101-002 (referred to as the parent study). About 370 subjects (with a maximum of 462 subjects) are expected to start the LTE. LTE subjects may be grouped into the following treatment groups:

- **Group 1 – Optimal Dose Treatment:** Subjects treated with the optimal dose throughout the parent trial and throughout their LTE participation.
- **Group 2 – Non-Optimal Dose Active Treatment, then Optimal Dose Treatment:** Subjects treated with active doses not selected as the optimal dose, who eventually will be treated with the optimal dose when this dose is selected.
- **Group 3 – Placebo to Non-Optimal Dose, then Optimal Dose Treatment:** Subjects originally assigned to the placebo arm during the parent trial then re-randomized to the two non-optimal active groups. Later, they will receive the optimal dose when it is selected.
- **Group 4 – Placebo to Optimal Dose Treatment:** Subjects originally assigned to the placebo arm during the parent trial then either re-randomized or switched to optimal dose.

Further characteristics of these LTE treatment groups are described in [Section 8.3](#).

Among the comparisons to consider are:

- 1) LTE levels and trends among subjects always on the optimal dose Group 1 will be compared in order with those of:
 - Group 4: Placebo to optimal dose treatment
 - Group 3: Placebo to non-optimal dose, then optimal dose treatment
 - Group 2: Non-optimal dose active treatment, then optimal dose treatment
- 2) Levels and trends in LTE safety and effectiveness endpoints for subjects always on the optimal dose (Group 1) will be compared to levels and trends during the parent study among these same subjects. This will be done to document whether the effects of the previous optimal dose on subsequent measures of effectiveness and safety while still undergoing treatment persist, improve, plateau, or dip the longer the duration of the optimal treatment.
- 3) Trends in continuous LTE effectiveness endpoints will be assessed separately for continuous dose intensity and continuous relative dose intensity.
- 4) Levels and trends in LTE safety and effectiveness after 24 weeks of optimal dose treatment in each of the four treatment groups will be reported.

Other comparisons will be outlined in the Statistical Analysis Plan.

The association of LTE AV-101 treatment groups with levels and trends in LTE safety will be explored with a continuous AV-101 treatment exposure based on average weekly dose intensity. Planned weekly dose intensity during the parent trial ranges from zero among those who only received placebo treatment, 140 mg/week among those randomized to 10 mg per dose BID, 490 mg/week among those randomized to 35 mg per dose BID and 980 mg/week among those randomized to 70 mg per dose BID. With dose titration, early treatment discontinuation, or missed doses, average dose intensity per week will be calculated by summing up AV-101 with the cumulative sum divided by the duration of treatment in weeks.

Safety and effectiveness endpoints collected while subjects are participating in the parent study will serve as the benchmark for safety and effectiveness endpoints collected during the LTE study. LTE levels of safety and effectiveness endpoints will be presented by LTE treatment groups and LTE visits intervals disaggregated by visits prior to or after subjects are dosed with the optimal dose. These safety and effectiveness levels will be presented using descriptive statistics applicable to continuous or categorical data. Trends or patterns over time in a select set of safety and effectiveness measures will be presented graphically. Continuous data will be summarized using the following descriptive statistics: number of observations, mean, standard deviation, standard error, median, minimum, and maximum. Categorical data will be summarized using frequencies and percentages.

Changes from baseline will be calculated as the later value minus the baseline value. Baseline will be defined for specific endpoints as the time prior to starting active treatment with AV-101 in either the LTE or the parent study. Baseline values for subjects will consist of the baseline values during the parent trial among subjects in the always active treatment groups (optimal dose [Group 1] or non-optimal dose [Group 2]). For subjects who are initially assigned to placebo in the parent

trial, baseline values consist of either Week 24 parent trial values or baseline LTE prior to re-randomization to active treatment.

Trends or patterns over time in safety and effectiveness measures will be presented using repeated measures data analysis methods applicable to categorical or continuous data. Time-to-event analyses will be performed using Cox models with time-independent and time-varying covariates, specifically, extent of AV-101 dose intensity as continuous or categorical variables. For time to event data like overall survival, the starting period is the day prior to the first dose in the parent trial. Kaplan-Meier procedures for time -to-event analysis will also be performed.

For longitudinal continuous variables, the shape of the effectiveness trajectory (trends), repeated measures models over time will be fitted to assess whether the effectiveness measure indicates waxing, waning or remaining persistently over time. During the LTE, visits may be grouped into before or after optimal dose is administered. Levels of the LTE effectiveness endpoints before or after optimal dose treatment during the LTE will be reported.

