5.5 Down Titration

If a subject down titrated the dose of AV-101 in Study AV-101-002 and successfully completed 24 weeks of treatment, the subject should begin the LTE study with 2 capsules BID at the assigned dose i.e., either re-randomized if coming from placebo or continuing on the randomized dose but at two capsules BID if on active. If the subject does not tolerate the 2 capsules, they may down titrate to one capsule in the LTE. At the time of optimal dose selection and the transition to the optimal dose in subjects who have down titrated in the LTE, the investigator should decide whether it is clinically appropriate to transition these subjects to the optimal dose given the tolerability history and optimal dose selection (Investigators will be unblinded to treatment dose at this time). E.g., if a subject in the 10 mg dose group has to down titrate to one capsule (5 mg) then it is likely inappropriate to transition the subject to 70 mg if that is the chosen optimal dose for Phase 3 and LTE; however, this decision should be based on the Investigator's opinion. Down titration to one capsule BID after being switched to the optimal dose in the LTE will be permitted.

If a subject develops intolerable adverse events during the study, a down titration from two capsules to one capsule will be allowed. The Investigator should conduct an Unscheduled telephone or video visit with the subject to discuss and decide whether down titration to a lower dose is warranted. Careful consideration should be made whether to down titrate or not, and the decision to down titrate should be made when the alternative would be to withdraw study treatment due to drug intolerability. The Investigator should capture any adverse or clinical worsening events, and in cases where the Investigator agrees that down titration is appropriate, the CRO Medical Monitor should be notified as soon as possible. Subjects will not be allowed to up-titrate after having down titrated.

If it is determined by the Investigator that down titration is warranted, the subject will be instructed to take only 1 capsule BID from the assigned study drug bottles. The date and reason for down titration must be recorded in the subject's source documents and in the eCRF.

Down titration is also required if an ECG reveals, for a subject, a QTc interval that exceeds 500 msec, or a QTc progression of ≥ 60 msec (see [Section 5.9.2](#)).

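### Average weekly dose intensity counts dosing after the adverse event, so the exploratory dose-safety association can be biased, in a direction that depends on which dose is chosen as optimal

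*Combined protocol and SAP*

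**What the plan says.** Section 8.1 states that the association of treatment with long-term safety "will be explored with a continuous AV-101 treatment exposure based on average weekly dose intensity". It gives a planned value of "140 mg/week among those randomized to 10 mg per dose BID"; the figures for 35 and 70 mg BID are 490 and 980 mg/week. For subjects who depart from plan (titration, stopping early, missing doses), the AV-101 actually taken is added up, "with the cumulative sum divided by the duration of treatment in weeks". No lag, pre-event window or assigned-dose version is stated.

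Other sections make dose depend on safety:
- Section 5.5: "If a subject develops intolerable adverse events during the study, a down titration from two capsules to one capsule will be allowed". Up-titration afterwards is not allowed.
- Sections 5.5 and 5.9.2: certain QTc findings require a dose reduction.
- Section 7.7: drug is withheld for confirmed Grade 3 findings judged related.
- Section 5.5: for subjects already down-titrated, the investigator decides whether they move to the optimal dose.

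Two further parts bear on the point. Section 8.1 also plans Cox models in which dose intensity may be a time-varying covariate. Section 8.6 displays safety by the four treatment groups, splits Groups 2 and 3 into non-optimal and optimal intervals, and compares repeated events between arms with a negative binomial model.

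**The concern.** A dose-safety analysis should relate an event to the dose taken before it. An average over all treatment also includes the dose taken after it, and here that later dose is often lower because of the event. Subjects with events then drift to lower exposure values whatever dose caused the event. This is reverse causation within the exposure definition.

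Long-term safety is the study's objective, and this is the continuous dose-safety analysis that Section 8.1 names. A slope that is too flat, or reversed, could be read as evidence that higher dose carries little risk. A slope that is too steep could be read as the opposite.

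**Working it through.** **1. The plan's own figures.** Weekly intensity = dose × 2 per day × 7 days: 10 × 14 = 140, 35 × 14 = 490, 70 × 14 = 980 mg/week. All three reproduce.

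**2. What one halving does.** A 70 mg BID subject has an event at week 12 of 48 and is halved:
(980 × 12 + 490 × 36) / 48 = 29,400 / 48 = 612.5 mg/week.
The event occurred at 980 mg/week but is analysed at about 612. Halved at week 4 of 24: (980 × 4 + 490 × 20) / 24 = 13,720 / 24 ≈ 572.

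**3. What stopping does.** The divisor is weeks of treatment. A 70 mg BID subject who stops at week 12 keeps 980 × 12 / 12 = 980. Dividing by 48 planned weeks would give 980 × 12 / 48 = 245. On a constant dose, stopping alone does not lower this exposure.

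**4. Fixed doses, simulated.** Any AE is regressed (logistic) on whole-period average intensity; odds ratios (ORs) are per 980 mg/week. The rates of AEs, halving and stopping are assumptions, because the documents give none.

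*48 weeks, n = 370, hazard 0.01/week at zero dose, 10% of AE subjects stop:*

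| AE subjects halved | No true effect | True hazard ratio 2 |
|---|---|---|
| 0% | 1.00 | 2.64 |
| 10% | 0.87 | 2.31 |
| 25% | 0.76 | 1.91 |
| 50% | 0.53 | 1.42 |
| 75% | 0.37 | 0.84 |

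The OR on assigned dose stays at about 1.0 and at 2.5 to 2.8 respectively. A reference OR above 2 is expected when events are common: (e^0.96 − 1) / (e^0.48 − 1) ≈ 2.6. A run with stopping but no halving gave 2.68 on both exposures.

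*104 weeks, true hazard ratio 2:* 2.4 on assigned dose; 2.15, 1.69 and 1.20 on average intensity with 10%, 30% and 60% halved. A hazard of 0.003/week at zero dose would imply the 2.4: (e^0.624 − 1) / (e^0.312 − 1) ≈ 2.37.

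**5. Adding the transition to one optimal dose.** 72 weeks, n = 370, switch between weeks 24 and 47, hazard 0.01/week at zero dose, halved subjects not switched, true hazard ratio 2. OR on average intensity:

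| Optimal dose | No AE-driven change | 25% halved, 10% stopped | 50% halved, 10% stopped | 30% stopped only |
|---|---|---|---|---|
| 10 mg | 3.02 | 3.82 | 3.59 | 6.75 |
| 35 mg | 3.42 | 1.12 | 0.50 | 2.83 |
| 70 mg | 2.89 | 0.35 | 0.10 | 0.73 |

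With no true effect and 25% halved, 10% stopped, the ORs are 1.36, 0.39 and 0.15. The sign depends on the optimal dose because subjects who stop, or who stay on a reduced dose, never average in the new dose. If the new dose is low they keep a high average; if it is high they keep a low one.

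**6. The alternative exposure.** In the same transition runs, a person-week Poisson model on the dose in force before the first event gave rate ratios of 0.98 to 1.04 (truth 1.0) and 1.90 to 2.04 (truth 2.0), whichever dose was optimal.

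**The case against.** **The analysis is exploratory.** This stands. Section 8.1 says so, and the Section 8.6 group summaries and negative binomial model do not use average intensity. A reader might infer that the main safety analysis is compromised; the documents do not support that.

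**Time-varying exposure is already foreseen.** Section 8.1 plans Cox models with dose intensity as a possible time-varying covariate, and Section 8.3 calls time-varying exposure a key characteristic. This narrows the gap but does not close it. A running average updated through the event interval can still include dosing after onset, and no lag is stated. The logistic regression used in the working is an illustration; the plan does not name a model for this exploration.

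**The direction is not fixed.** This stands. A reader might infer that dose will look safer than it is. That follows for AE-driven halving with fixed doses or with 35 or 70 mg as optimal, but not with 10 mg.

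**Early stopping.** A reader might also infer that dividing by treatment weeks hides harm among early stoppers. On a constant dose it does not lower their average (step 3). Stopping matters only in combination with the transition (step 5, last column).

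**Down-titration may be uncommon.** Section 5.5 reserves AE-driven reduction for cases where the alternative is withdrawing treatment, and Section 4.1 excludes subjects whose study drug was stopped for treatment-limiting toxicity in the parent study. At 10% halved with fixed doses the attenuation is modest: 2.31 against 2.64.

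**Assigned dose is no simple cure.** This stands. After transition the originally assigned dose no longer describes exposure. With a true hazard ratio of 2, 104 weeks, transition at week 36 and hazard 0.003/week, its OR was only 1.3 to 1.4.

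**Conclusion.** The concern holds as a bias in an exploratory analysis. Applied as written, the rule gives an exposure that the outcome alters, and the plan states no safeguard. Under fixed doses with a true hazard ratio of 2, the OR falls from about 2.4 to about 2.15, 1.7 and 1.2 at 10%, 30% and 60% halved. With the transition, the distortion can be large: it ran towards or past the null in the halving runs when 35 or 70 mg was optimal, and away from it when 10 mg was. A separate 104-week run gave 5.3 to 6.2 for 10 mg, so the size is sensitive to assumptions.

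The documents do not support saying that dose will look harmless or protective, because neither the optimal dose nor the down-titration rate is known. The good recovery in step 6 applies to first events; dose changes followed the first event, and subjects did not differ in susceptibility. It should not be read as proof for repeated events, where earlier events influence later dose.

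**What to change.** Specify in the SAP, for every dose-safety analysis:

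1. **Main exposure:** the time-updated dose in force before each interval, lagged so that only dosing before AE onset counts. Use it in the time-varying Cox model that Section 8.1 already plans, or in a count model split by dose interval. For repeated events, state how earlier events are handled.
2. **Supporting analysis:** assigned dose, restricted to the period before transition to the optimal dose.
3. **Description only:** whole-period average dose intensity, reported as an exposure summary and not as a predictor of safety events.

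The cost is SAP wording and splitting each subject's data by dose interval. Section 5.5 already requires the date and reason of each down-titration in the eCRF. Missed doses are known only from returned drug at clinic visits (Section 5.8), so their timing will be coarse. The Section 8.6 negative binomial model uses total weeks as its offset, so an interval-split count model would be an additional analysis and not a change of wording alone.
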